11.5.2.2 LogMAR

Analysis for European Medicines Agency

The primary analysis will be performed on the intent-to-treat (ITT) population. The change from baseline to each follow-up visit in the LogMAR acuity will be the response. The change from baseline of all-GS010 eyes will be compared to the change from baseline of all-sham eyes (intra-subject comparison) using a mixed-effects ANCOVA model using the following terms (or covariate) in the model:

- Subject and eyes of the subject as random factors
- The baseline LogMAR
- Treatment

The investigative site will not be included in this analysis as the number of subjects recruited per site will be very small. However, stratification by geographical area will be performed as a sensitivity analysis. Neighboring countries can be pooled to reach at least 9 subjects per geographical entity. The analysis will be performed based on alpha of 0.05 (two-sided test).

An additional model will add the treatment by geographical interaction to investigate lack of generalizability of the treatment effect.

Analysis for Food and Drug Administration

The primary analysis will be performed on the ITT population. The change from baseline of the best-GS010 treated eyes will be compared to the change from baseline of the best-sham eyes (inter-subject comparison) using an ANCOVA with baseline LogMAR as covariate. The analysis will be performed using an alpha of 0.05 (two-sided test). The statistical significance in favor of the best-GS010 treated eyes against the best-sham eyes will show evidence of the advantage of using GS010 for halting visual acuity loss or improving visual acuity in subjects with LHON. The difference in the mean change from baseline (adjusted mean difference) between the two treatment groups and associated 95% confidence interval will be reported.

The center will not be included in the analysis as the number of subjects recruited per site will be very small. However, stratification by geographical area will be performed as a sensitivity analysis. Neighboring countries can be pooled together to reach at least 9 subjects per geographical entity. The pooling of countries will be performed during the masked review of data.

An additional model will add the treatment by geographical area interaction to test for a lack of generalizability of the treatment effect.

The same analysis will be repeated for worst-GS010 treated eyes against worst-sham eyes.

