In the RESCUE/REVERSE studies, both eyes received standard antiseptic preparation, were administered topical local ocular anesthetic agents, and had pupillary dilation. Administration of an intraocular pressure-lowering agent preceded treatment. GS010 was administered once during the study via a single intravitreal (IVT) injection. Sham IVT injection was performed by applying pressure to the eye at the location of a typical procedure using the blunt end of a syringe without a needle. The right eye of each subject was randomly allocated to receive either GS010 or sham treatment in a 1:1 allocation ratio. The fellow (left) eye received the treatment not allocated to the right eye. Therefore, each subject received GS010 in one eye and sham treatment in the fellow eye.

The schema of the study design of the RESCUE/REVERSE studies is given below:

[figure not shown]

An algorithm with a testing hierarchy was employed to determine the best- and worst-seeing eye of each subject prior to randomization. The randomization was based on the right and left eye, because if the right eye was treated, the left eye would receive sham and vice versa, so the treatments were automatically balanced. However, the best- or worst-seeing eye at entry could have been a confounding factor, and it could not be excluded that the treatment effect would not be the same in the best and worst seeing-eye. In order to test this hypothesis with optimal power, an adaptive randomization technique called Efron's minimization¹⁰ method was used to minimize the imbalance of treatment groups between the best-seeing eyes and worst-seeing eyes.

Masking was accomplished with sham injection of the fellow eye. Thus, treatment allocation was double-masked for both the subject and the investigation (follow-up) team, except the physician and medical team that performed the GS010 administration and sham injection and the first follow-up visit. Centralized analysis of the Early Treatment Diabetic Retinopathy Study (ETDRS) visual acuity results, automated visual fields, SD-OCT, color vision and contrast sensitivity was performed by a masked central reading lab.

The schematic design of this long-term follow-up non-interventional study is given below:

Figure 1: Study Design Schematic of the Long-Term Follow-up of Subjects from the RESCUE and REVERSE Clinical Studies

Note: Inclusion into the long-term follow-up study will be allowed from Week 96 of the RESCUE/REVERSE studies up to 1 day prior to Year 2.5.

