4.3 SECONDARY EFFICACY ENDPOINTS

The secondary efficacy endpoints are:

- Change in contrast sensitivity measured with the Pelli-Robson chart in all-, best-, and worst-eyes treated with GS010 IVT injection compared to all-, best-, and worst-eyes treated with sham IVT injection respectively to the follow-up study time points (2, 3, 4, and 5 years).
- Change in best-corrected visual acuity (BCVA) reported with Logarithm of the Minimal Angle of Resolution (LogMAR), change of parameters measured with Humphrey™ visual field (HVF) 30-2, and change of parameters measured with spectral-domain optical coherence tomography (SD-OCT) in all-, best- and worst-eyes treated with GS010 IVT injection compared to all-, best-, and worst-eyes treated with sham IVT injection respectively to each follow-up study time points (2, 2.5, 3, 4, and 5 years).
- Response status of eyes treated with GS010 IVT injection compared to eyes treated with sham IVT injection, including all-, best- and worst-eyes receiving GS010 or sham respectively, with responder eyes defined by:
 - An improvement of at least 15 ETDRS letters (equivalent to a decrease of at least 0.3 LogMAR) compared to baseline, or having a Snellen acuity equivalent better than 20/200.
 - Eyes that lose less than the 15 ETDRS letters (equivalent to an increase of less than 0.3 LogMAR) compared to baseline.
- Response status of subjects whose ETDRS scores of the treated eye are at least 15 letters better than the sham eye or whose treated eye has a LogMAR acuity of at least 0.3 LogMAR better than the sham eye at each long-term follow-up visit (2, 2.5, 3, 4, and 5 years).
- Visual improvement as measured by LogMAR to determine the difference in improvement (LogMAR) for all-GS010 eyes compared to all-sham eyes, for best-GS010 eyes compared

to best-sham eyes, and for worst-GS010 eyes compared to worst-sham eyes, with comparisons to baseline at each follow-up study time point (2, 2.5, 3, 4, and 5 years).

- Change of ganglion cell layer (GCL) volume and other parameters measured by SD-OCT for all-GS010 eyes compared to all-sham eyes, for best-GS010 eyes compared to best-sham eyes, and for worst-GS010 eyes compared with baseline at each follow-up study time point (2, 2.5, 3, 4, and 5 years).
- QoL as measured with the Visual Functioning Questionnaire 25 (VFQ-25), with change from baseline at each follow-up study time point (2, 2.5, 3, 4, and 5 years).

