8.5.1 Primary Efficacy Variable

Not applicable for this study.

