8.5.2.2 LogMAR

Eye Level

Mean LogMAR BCVA will be summarized at each follow-up visit (Years 2, 2.5, 3, 4 and 5), along with mean change from baseline to each follow-up visit.

This summary comparing all-GS010 eyes to all-sham eyes will be repeated by comparing best-GS010 eyes to best-sham eyes and worst-GS010 eyes to worst-sham eyes.

These summary tables will be reproduced for those eyes with on-chart BCVA at baseline.

The curves of change from baseline at each time point for treated and sham eyes will be produced, with both sham and treated curves on same graph

The curves of absolute BCVA values at each time point for treated and sham eyes will be produced with both sham and treated curves on same graph.

LogMAR BCVA will be analyzed by using two approaches:

For the EMA, the change of LogMAR from baseline to the visit of interest will be compared between all-GS010 treated eyes and all-Sham treated eyes using a mixed-effects analysis of covariance (ANCOVA), with baseline LogMAR as a covariate, and subject and eyes of the subject as random factors.

The FDA has recommended comparing GS010 vs Sham in the Best-seeing eyes as a primary analysis. Therefore, change of LogMAR from baseline to the visit of interest will be compared between Best-GS010 treated eyes and Best-Sham treated eyes for the FDA. ANCOVA will be used for this analysis.

The EMA analysis is based on intra-subject comparison of change of LogMAR from baseline to the visit of interest. For FDA, the analysis is based on inter-subject comparison of change of LogMAR from baseline.

For eyes with on-chart BCVA at baseline, the change of LogMAR from baseline to the visit of interest will be analyzed between GS010-treated eyes and Sham-treated eyes.

At each visit of interest, the following analyses related to Nadir BCVA will be performed:

- The change from Nadir BCVA will be calculated for each eye of each subject and will be expressed in LogMAR.
- The time to Nadir BCVA will be calculated for each eye of each subject and will be expressed in Weeks.
- The mean LogMAR change from Nadir will be assessed for all eyes, all GS010 eyes and all sham eyes.
- The mean time to Nadir BCVA will be assessed for all eyes, all GS010 eyes and all sham eyes.

Subject Level

At subject level, the best outcome observed in either eye will be considered. The following summaries will be presented:

- The change of LogMAR BCVA from baseline to the visit of interest

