- The change of LogMAR BCVA from nadir to the visit of interest

Analysis for European Medicines Agency (EMA)

The primary analysis will be performed on the mITT Population. The change from baseline to each follow-up visit in the LogMAR acuity will be the response. The change from baseline of all-GS010 eyes will be compared to the change from baseline of all-sham eyes applying a mixed-effects ANCOVA model using the following terms (or covariate) in the model:

- Subject as a random factor.
- The baseline LogMAR as a covariate.
- Treatment as a fixed effect.

The null and alternative hypotheses for the EMA LogMAR analysis are:

$$H_0: \mu_{\text{All-GS010}} = \mu_{\text{All-Sham}}$$

$$H_1: \mu_{\text{All-GS010}} \neq \mu_{\text{All-Sham}},$$

where μ presents the mean change from baseline to the visit of interest in LogMAR and “All” represents all eyes treated with GS010 or Sham.

The investigative site will not be included in the analysis as the number of subjects recruited per site will be very small. However, stratification by geographical area may be performed as a sensitivity analysis. Neighboring countries can be pooled to reach at least 9 subjects per geographical entity. The analysis will be performed using an alpha of 0.05 (two-sided test).

An additional model may add the treatment by geographical interaction (geographical areas: USA and Europe) to investigate the generalizability of the treatment effect. The following model diagnostics may be checked: normality of error terms, independence of error terms, independence of the covariate and treatment effect, and homogeneity of error variances.

Analysis for Food and Drug Administration

The primary analysis will be based on the mITT Population. The change from baseline of the best-GS010 treated eyes will be compared to the change from baseline of the best-sham eyes (inter-subject comparison) using an ANCOVA with baseline LogMAR as covariate. The analysis will be performed using an alpha of 0.05 (two-sided test). The statistical significance in favor of the best-GS010 treated eyes against the best-sham eyes will show evidence of the advantage of using GS010 for halting visual acuity loss or improving visual acuity in subjects with LHON. The difference in the mean change from baseline (adjusted mean difference) between the two treatment groups and associated 95% confidence interval will be reported.

The null and alternative hypotheses for the FDA LogMAR analysis are:

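### SAP 8.5.2.2 leaves out the worst-eye LogMAR ANCOVA that the protocol requires, without declaring it, so the best-eye result has no adjusted worst-eye difference beside it

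*SAP*

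**What the plan says.** **Protocol.** Endpoint 8 (Protocol 7.2.2) asks for ANCOVA of LogMAR improvement in all, best and worst eyes at each follow-up time point. Protocol 11.5.2.2 describes the best-eye ANCOVA for the FDA and ends: "The same analysis will be repeated for worst-GS010 treated eyes against worst-sham eyes".

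**SAP.** Section 4.3 keeps the endpoint in all three groups, including "and for worst-GS010 eyes compared to worst-sham eyes". Section 8.5.2.2 then describes two analysis approaches:

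- all eyes, within subject, for the EMA;
- best eyes, between subjects, for the FDA. On this it says "The FDA has recommended comparing GS010 vs Sham in the Best-seeing eyes as a primary analysis".

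Hypotheses are written for those two only. Worst eyes appear in 8.5.2.2 only in the summary of means and mean changes. On the best-eye test the SAP says "The statistical significance in favor of the best-GS010 treated eyes against the best-sham eyes will show evidence of the advantage of using GS010", and the sentence goes on to name subjects with LHON as those it applies to. That wording is carried over from Protocol 11.5.2.2.

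Section 8.8 lists the changes from the protocol's analyses and does not mention the worst-eye ANCOVA. On a primary efficacy variable, SAP 8.5.1 says "Not applicable for this study". SAP 8.5.4 makes all efficacy analyses secondary, without multiplicity adjustment.

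**The concern.** By design, "each subject received GS010 in one eye and sham treatment in the fellow eye". The subjects who make up the best-GS010 group are therefore the same people who make up the worst-sham group, and the best-sham subjects are the worst-GS010 subjects. The best-eye and worst-eye contrasts compare the same two groups of people with the treatment labels exchanged.

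Suppose one group happens to contain more people who recover naturally. GS010 then looks good in best eyes and poor in worst eyes, or the reverse. A real effect in both eyes pushes both contrasts the same way. The worst-eye adjusted difference is therefore unusually informative about how to read a best-eye result, and it is the one that SAP 8.5.2.2 does not specify. What is at stake is a best-eye finding reported as an advantage for LHON subjects in general without that estimate next to it.

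**Working it through.** The documents give no sample size, SD, effect size or between-eye correlation for this comparison, so there is no design figure to reproduce.

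**Inputs.** Two-sided alpha 0.05 (SAP 8.5.2.2), so the critical value is 1.96. One GS010 eye and one sham eye per subject (SAP 3.1). Randomisation was 1:1 with balancing over best and worst eyes (SAP 3.1), so I take two equal groups of n. *Assumed:* equal variance s² of change in best and worst eyes, and within-subject correlation rho of the two eyes' changes, shown over a range.

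**Sign of rho.** Protocol 5.1 describes a bilateral disease. It also cites natural-history improvement of at least 15 letters in 14.7% of eyes, found in 18% of patients. With two study eyes per patient (assumed) and independent eyes, 1 − 0.853² = 27.2% of patients would have had at least one improved eye. The lower 18% suggests that improvement clusters within patients. This supports a positive rho but does not fix its size.

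**Algebra.** Let group A have GS010 in the best eye and group B have GS010 in the worst eye. Orient changes so that positive favours GS010.

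- D_best = mean_A(best) − mean_B(best); D_worst = mean_B(worst) − mean_A(worst).
- Var(D_best) = Var(D_worst) = 2s²/n.
- Cov(D_best, D_worst) = −rho·s²/n − rho·s²/n = −2·rho·s²/n.
- Hence corr(D_best, D_worst) = −rho.
- D_all = (D_best + D_worst)/2, and corr(D_best, D_all) = √((1 − rho)/2).

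**After a chance best-eye win.** Under no effect, P(Z_best > 1.96) = 0.025 whatever rho is. Given such a win:

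- E[Z_worst] = −rho × φ(1.96)/0.025 = −rho × 0.05845/0.025 = −2.338 × rho.
- P(worst-eye estimate against GS010) = P(Z_best > 1.96, Z_worst < 0)/0.025, from the bivariate normal with correlation −rho. The other columns are obtained in the same way.

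| rho (assumed) | Expected worst-eye z | Worst-eye estimate against GS010 | Worst eye significantly against | All-eyes test significant for GS010 |
|---|---|---|---|---|
| 0.3 | −0.70 | 77% | 9.5% | 24.3% |
| 0.5 | −1.17 | 91% | 18.5% | 18.5% |
| 0.8 | −1.87 | 99.8% | 43.9% | 10.1% |
| 0.9 | −2.10 | about 100% | 59.3% | 7.1% |

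**Check with baseline adjustment.** I simulated ANCOVA with baseline as covariate, 200,000 runs per setting, for assumed totals of 40, 60 and 76 subjects. The assumed baseline correlation between eyes was 0.7 and the slope of change on baseline −0.3. The correlation of the two estimates was −0.30 at rho 0.3, −0.50 at rho 0.5, and −0.79 to −0.80 at rho 0.8. After a best-eye win, the worst-eye estimate was against GS010 in about 77%, 90 to 91% and 99.7 to 99.8% of cases. The formula therefore holds for the planned type of model.

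**The case against.** **It may not be dropped at all.** A reader might infer that the SAP has removed the worst-eye test. The documents do not go that far. SAP 4.3 keeps the comparison, SAP 8 says in general terms that every continuous endpoint gets an ANCOVA, SAP 6.4 defines a worst-eye subset, SAP 8.5 allows analyses in subsets as appropriate, and the SAP is to be read with the protocol. This stands: the SAP is inconsistent, and removal is not shown. It does not settle the matter, because the general ANCOVA sentence is not applied literally elsewhere. Humphrey field parameters (8.5.2.5) and quality of life get summaries only. Where worst-eye inference was intended, for responders in 8.5.2.4, the SAP says so.

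**Checks remain.** A reader might also infer that a chance best-eye win would go unchecked. That is too strong. The SAP keeps worst-eye LogMAR summaries, a worst-eye responder logistic regression (8.5.2.4), the all-eyes ANCOVA and an exploratory eye-status-by-treatment interaction (8.7.1). The table shows that the all-eyes test would fail to support most chance best-eye wins. With equal groups and before covariate adjustment, D_worst = 2·D_all − D_best, so the point estimate could be recovered. What is missing is narrower: a specified, baseline-adjusted GS010-minus-sham difference in worst eyes with its interval. The confidence interval promised in SAP 8 is for change from baseline, and the responder model addresses a different endpoint.

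**No error rate is inflated.** The best-eye test has the same 0.05 level with or without a worst-eye test. This stands in full.

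**The conclusion sentence is the protocol's.** This also stands; the SAP did not introduce it. But the protocol follows it with the worst-eye repeat, and the SAP does not.

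**A gate would go too far.** One might want the best-eye claim to require a significant all-eyes result. The documents present the two as separate analyses for separate regulators in a study whose primary objective is safety, and a gate would cost power if benefit were confined to best eyes. I do not propose it.

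**Conclusion.** The point holds in a limited form. SAP 8.5.2.2 omits an analysis required by Protocol 11.5.2.2 and protocol endpoint 8, sits uneasily with SAP 4.3 and SAP 8, and is not covered by the list in SAP 8.8. Because of the paired-eye design, the omitted estimate is a strong diagnostic for a best-eye result: with no effect, about 77% of chance best-eye wins at rho 0.3 and 91% at rho 0.5 would show a worst-eye estimate against GS010.

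Those percentages rest on an assumed rho, equal variances and balanced groups. The −rho relation follows from the design under the last two assumptions. At rho 0 the worst-eye estimate would be against GS010 in half of such wins, and the contrasts become exact opposites only at rho 1. The documents do not support reading this as an inflated type I error or as the absence of any check.

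**What to change.** In SAP 8.5.2.2:

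1. Restore the worst-eye ANCOVA of change in LogMAR with baseline LogMAR as covariate, as in Protocol 11.5.2.2, and state its hypothesis. If it is deliberately not to be run, list and justify that in SAP 8.8 and align SAP 4.3.
2. Report the best-eye, worst-eye and all-eyes adjusted differences with 95% confidence intervals side by side at each visit.
3. Word a significant best-eye result as evidence for best-seeing eyes, to be read with the other two estimates.

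An eye-status-by-treatment term in the all-eyes model is optional, since 8.7.1 already plans to explore that interaction. If it is used, it is a better guide to whether the effects differ than two separate p-values.

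The cost is one more model per visit on data already collected, and a narrower conclusion from the best-eye test.
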